Efficacy of Two Novel Behavioral Post-cessation Weight Gain Interventions

NCT03156660

Document Uploaded 21APR2022

Document Created 10NOV2020

1. Purpose

Although smoking cessation accrues significant health benefits, regardless of the duration of smoking (4, 25, 26), it is typically accompanied by weight gain. A recent meta-analysis quantified this weight gain as, on average, 1.1 kg, 2.3 kg, 2.9 kg, 4.2 kg, and 4.7 kg at 1, 2, 3, 6, and 12 months after quitting, respectively (9). Concerns about postcessation weight gain are common and are often cited as a reason to delay cessation attempts (10, 11); furthermore, postcessation weight gain is associated with smoking relapse (10-12).

While there is some ongoing debate (13-15) about the effectiveness of behavioral weight management programs in conjunction with smoking cessation programs, it appears that behavioral weight management programs have not been able to successfully reduce postcessation weight gain (16). In addition, contrary to popular belief, there was no indication that involvement in weight management programs impacted abstinence (16, 17). Moreover, while some short-term weight gain attenuation has been observed with some pharmacotherapies (e.g., nicotine replacement therapy, varenicline), there is no long-term weight gain prevention benefit for any of the pharmacotherapies (27-30).

Much like weight maintenance after weight loss has proven to be challenging (18), weight maintenance after smoking cessation has been difficult to achieve. In a trial unrelated to postcessation weight gain, Wing and colleagues (19) hypothesized that making small, consistent changes may be beneficial for weight gain prevention. Wing *et al.* (19) tested this hypothesis in a recent study and found that participants who received their 'Small Changes' intervention gained significantly less weight as compared to the control group. Given these positive results, this approach may be translated to interventions focusing on other individuals at high risk for weight gain (i.e., those who are about to undertake smoking cessation).

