Our hypotheses include that randomization to the SMALL and LOSS conditions will produce smaller post-cessation weight gain compared to participants in the BIBLIO condition. The main independent variable of interest will be treatment assignment and the outcome will be weight change from baseline to 12-month follow-up. Measures of weight will be obtained at multiple time points to provide feedback, but we will model only the final measure to capture full post-cessation weight gain. Two separate general linear and mixed ANCOVA-like regression models for continuous measures will be utilized, with treatment effect estimated as the distance between the fitted group-specific means at the 12-month data collection visit (SMALL compared to BIBLIO and LOSS compared to BIBLIO), while adjusting for the fitted distance between them at baseline. In addition, we will adjust within the model for demographic factors, baseline weight, and other covariates if needed; however, due to randomization, we do not anticipate significant differences in baseline distributions. We will also test the interactions between treatment assignment and demographic covariates to examine the homogeneity of treatment effects. We will include smoking status within our modeling strategy either as moderator or a confounder. We hypothesize no significant difference in post-cessation weight gain between the SMALL and LOSS conditions. We will compare the two conditions within the scope of the regression models described previously. The main treatment comparison results will be considered significant at $\alpha = .017$ due to three pre-planned contrasts, with all other associations at $\alpha = .05$.

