We hypothesize that participants randomized to the SMALL, LOSS, and BIBLIO conditions will have similar rates of smoking cessation at 12-month assessment. Given that the outcome is binary (i.e., prolonged abstinence; yes or no) and the treatment conditions are nominal, we will use categorical analytical methods. To test the differences in prolonged abstinence between the intervention arms, we will apply χ^2 test and then a multivariate logistic regression model, with BIBLIO selected as the referent group compared to the other conditions. We will estimate the relative odds of a treatment effect on prolonged abstinence while adjusting for baseline demographics, smoking history (e.g., onset of regular smoking, quit attempts, use of tobacco products), process measures and other potential confounders. As such, we can test the associations and estimate effects of additional variables, besides treatment effect.

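### Two hypotheses of no difference (SMALL v LOSS weight gain; abstinence in all three arms) have only tests of difference as criteria, so an imprecise null result would nominally satisfy both

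*SAP*

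**What the plan says.** Both hypotheses are in the SAP, Statistical Analysis. SMALL, LOSS and BIBLIO are the protocol's Groups 1, 2 and 3.

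- **Weight.** The SAP writes "We hypothesize no significant difference in post-cessation weight gain between the SMALL and LOSS conditions". The analysis given for it is one sentence: "We will compare the two conditions within the scope of the regression models described previously". The main treatment comparisons are judged at .017, "due to three pre-planned contrasts, with all other associations at" .05. The treatment effect is estimated as a distance between fitted group means at 12 months.
- **Abstinence.** Participants in the three arms "will have similar rates of smoking cessation at 12-month assessment". The analysis reads "To test the differences in prolonged abstinence between the intervention arms, we will apply" a chi-square test and then a logistic model, "with BIBLIO selected as the referent group compared to the other conditions". An effect measure is planned: "We will estimate the relative odds of a treatment effect on prolonged abstinence". Abstinence is not one of the three main contrasts, so its level is .05.

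Neither document gives an equivalence or non-inferiority margin, an equivalence test, an interval rule, a definition of similar, or a power or precision calculation.

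**The concern.** A test of difference can reject equality but cannot establish it. The weight hypothesis is worded so that any p-value above .017 agrees with it, and the stricter threshold makes that easier to reach than .05 would. Abstinence has no criterion beyond its tests. In both cases a smaller or noisier trial is more likely to agree with the hypothesis.

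What is at stake is the reading of two secondary statements: that the two active programmes control weight equally well, and that adding a weight programme does not affect quitting. The second matters because the protocol's Purpose section raises that question when it reviews earlier work.

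**Working it through.** **Inputs from the documents.** Planned arms are 160/160/80 (Protocol, section 5); 400 split 2:2:1 gives exactly that. Alpha is .017, which is .05/3 = .0167 rounded. For scale, the protocol's Purpose section cites average gains ending "4.2 kg, and 4.7 kg at 1, 2, 3, 6, and 12 months after quitting, respectively". The sample size of 400 cannot be reproduced, because no SD, abstinence rate, effect size or power accompanies it.

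**Assumptions.** Two-sided tests; no attrition; SD of 12-month weight change 6 kg (range 5-7); BIBLIO abstinence 30% (range 20-40%).

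**Weight, SMALL v LOSS.**
- z for two-sided .017 = 2.387.
- SE = 6 × √(2/160) = 0.671 kg.
- Largest non-significant observed difference = 2.387 × 0.671 = 1.60 kg (1.33 at SD 5, 1.87 at SD 7).
- Chance that a true 1.5 kg difference (1.5/4.7 = 32% of the cited 12-month gain) is non-significant = Φ(2.387 − 1.5/0.671) = Φ(0.151) = 56% (38% at SD 5, 68% at SD 7).
- An observed 1.5 kg would have a 98.3% CI of 1.5 ± 1.60, or −0.10 to 3.10 kg. That is no significant difference, yet 3 kg is not excluded.

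**Abstinence, an example of an imprecise null.** Take 32/160, 32/160 and 24/80 abstinent (20%, 20%, 30%).
- Pearson chi-square = 3.73 on 2 df, p = .155.
- Each active-minus-BIBLIO difference is −10 points, SE = √(.2×.8/160 + .3×.7/80) = .0602, 95% CI −21.8 to 1.8 points.
- Unadjusted odds ratio 0.58 (0.32 to 1.08).

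**Abstinence, how often a true 10-point deficit in both active arms goes undetected.**
- Chi-square alone: the pooled rate is 88/400 = .22, so the noncentrality is [320 × .02² + 80 × .08²]/(.22 × .78) = 3.73. The chance of falling below the 5% critical value of 5.99 is 61% (41% and 68% for BIBLIO at 20% and 40%).
- Chi-square and both unadjusted logistic (Wald) comparisons with BIBLIO all non-significant at .05, by simulation of 200,000 trials: 46% (31% and 54%). This is the fairer figure, since the SAP plans both steps.

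**Sensitivity to arm size.** Section 5 of the protocol allows more even allocation in waves under 40. The table uses SD 6 kg and a 30% BIBLIO rate.

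| Arms | Weight, true 1.5 kg missed | Chi-square alone | Chi-square plus both logistic |
|---|---|---|---|
| 160/160/80 | 56% | 61% | 46% |
| 133 per arm | 64% | 50% | 37% |
| 128/128/64 (20% loss) | 65% | 68% | 53% |

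**The case against.** The best defence is that no wrong inference is planned. Both statements are predictions, and nowhere does the SAP say that a p-value above its threshold will be reported as similarity. It also plans estimates. In the abstinence example the planned odds ratio, shown with its interval of 0.32 to 1.08, would reveal the imprecision at once. SMALL v LOSS abstinence, which a BIBLIO-referent model does not print by default, is one contrast from the same fit.

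Most of this stands, and it limits the point. A reader might infer that the SAP commits itself to treating non-significance as proof of similarity, or that similar and inconclusive results could not be told apart. The text supports neither: the first is not written, and the planned estimates would go a good way towards separating the two. What the defence does not supply is a criterion. Intervals are not mentioned for either hypothesis, nothing says how narrow they must be, and the weight hypothesis is itself phrased in terms of significance. A null result of any width fits the plan as written.

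The defence is also right that the 61% for chi-square alone overstates how often the whole abstinence plan would find nothing; 46% is the better guide.

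**Conclusion.** The point holds as a mismatch between hypothesis and criterion, and should be fixed. It follows from the SAP's wording and does not depend on any assumed figure. The assumed figures show only that an imprecise null is realistic at the planned size: about 56% (38-68%) for a true 1.5 kg weight difference, and about 46% (31-54%) for a true 10-point abstinence deficit in both active arms. The abstinence simulation uses unadjusted models, so the SAP's covariate-adjusted model could give somewhat different values.

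A reader might extend this to the trial's efficacy conclusions. That does not follow: SMALL v BIBLIO and LOSS v BIBLIO for weight are superiority questions, for which tests of difference are appropriate.

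**What to change.** **Main change.** Reword both hypotheses as estimation aims.
- Report the SMALL-LOSS weight difference with the 98.3% CI that matches the .017 test.
- Report all three pairwise abstinence comparisons, including SMALL v LOSS, as adjusted odds ratios with 95% CIs, adding risk differences.
- State that non-significance alone will not be read as similarity and that the conclusion will rest on the interval. This leaves room for a tight interval around zero to be described as such.

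**Optional.** Claim similarity only if a justified margin and the CI level for each outcome are fixed before any 12-month data are compared by arm, and the CI lies wholly within the margin. If arms have already been compared, only the main change applies.

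**Cost.** SAP wording, one extra contrast and a few outputs; no new data. The price is that similarity becomes harder to claim. The margins below are assumptions, with equal true outcomes at 160/160/80.
- Weight, SD 6 kg, power = 2Φ(m/0.671 − z) − 1. For a 2 kg margin it is 82% with a 90% CI (z = 1.645) and 69% with a 95% CI (z = 1.960). For 1.5 kg it is 45% and 22%.
- Abstinence, 30% rate, 10-point margin, 160 v 80: SE = √(.3×.7×(1/160 + 1/80)) = .0627. Non-inferiority power against BIBLIO = Φ(.10/.0627 − z) = 36% at one-sided .025 and 48% at one-sided .05.
- Two-sided abstinence equivalence within 10 points is unrealistic at 160 v 80. The 90% CI half-width is 9.0, 10.3 and 11.0 points at rates of 20%, 30% and 40%, so even at 20% a single comparison has only about 14% power.

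Interval reporting without a similarity claim is therefore the practical choice for abstinence, and possibly for weight.

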The biostatistician will randomize the participants to one of the three study conditions. Participants (n=400) will be randomly assigned in a ratio of 2 (Group 1, n=160): 2 (Group 2, n=160): 1 (Group 3, n=80). However; when less than 40 participants are recruited for a wave, the biostatistician will more evenly distribute the participants. Participants will be asked to complete another remote study visit for their randomization assignment and to meet their interventionist. Prior to this visit, participants will be mailed their study materials. After this visit, participants will be asked to weigh again on the BodyTrace scale.

Weight Management Interventions. Participants will complete their randomly assigned weight management intervention before initiating the smoking cessation intervention.

Weight Stability Condition (Group 1). Participants will be asked to keep their weight stable during the initial 8 weeks of the study.

Intervention Components:

- 1) Participants will receive **lesson materials** adapted from the Small Changes intervention (19).
- 2) As frequent weighing is a key component to this and most weight management programs (82), participants will be encouraged to engage in **daily weight self-monitoring** on the BodyTrace™ e-scale (<http://www.bodytrace.com/>), which they will be given at randomization. Each time a participant weighs, the e-scale will upload the weight automatically to a secure database, so that timely tailored feedback on weighing frequency/progress can be provided by the interventionist through email.
- 3) Participants will be provided with **Fit Bit activity trackers** to self-monitor their steps, consistent with the Small Changes intervention.
- 4) If subjects are randomized to Group 1, they will receive via mail a small reward valued less than two dollars, each week during the weight and smoking cessation sessions, then monthly during the booster

sessions, if they maintain their baseline weight or maintain a weight that is less than 1.4 kilograms above their baseline weight.

Weight Loss Condition (Group 2). Participants will be asked to achieve a weight loss goal of at least 5% of their baseline weight by week 8.

Intervention Components:

- 1) Participants will receive **tailored calorie and fat goals** based on their baseline weight (83).

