Efficacy of Two Novel Behavioral Post-cessation Weight Gain Interventions

NCT03156660

Document Uploaded 21APR2022

Document Created JAN2019

Statistical Analysis

All of the analyses will be performed with SAS/STATv14.1. Data will be examined for distributional normality and outliers prior to any analyses. Descriptive statistics will be generated for all variables of interest included in the analysis, overall and by treatment arm. Univariate comparisons will consist of χ^2 tests and ANOVA. We will use similar analytical methods to compare baseline characteristics between study completers and non-completers at 12 months. Based on these findings appropriate adjustments will be implemented in the regression models.

Consistent with previous studies, outcomes will be analyzed on an intention-to-treat basis, including available data from all randomized cases, regardless of treatment adherence and smoking status. Missing outcome data will be imputed using Markov Chain Monte Carlo model based approach by treatment arm. Monotone missing data pattern will be created by using all available measured outcome data points. This approach is most suitable for an arbitrary missing data mechanism.

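### The flat .017 level for the three weight contrasts is valid but conservative; a stepwise rule on one three-arm model would add power at the same 5% family-wise error

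*SAP*

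**What the plan says.** The SAP's Statistical Analysis section hypothesizes that "randomization to the SMALL and LOSS conditions will produce smaller post-cessation weight gain compared to participants in the BIBLIO condition". For the third pair it states: "We hypothesize no significant difference in post-cessation weight gain between the SMALL and LOSS conditions". Together these are all the pairwise comparisons among three arms.

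The error rule is a single step: "The main treatment comparison results will be considered significant at" .017, "due to three pre-planned contrasts, with all other associations at" .05. Neither document gives a stepwise or gatekeeping rule.

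On the model, "The main independent variable of interest will be treatment assignment", and the intention-to-treat analysis is described as "including available data from all randomized cases". The SAP also says "Two separate general linear and mixed ANCOVA-like regression models for continuous measures will be utilized", with covariates added if needed and smoking status entering as moderator or confounder.

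The Protocol (Study Project Procedures) plans for participants to be "randomly assigned in a ratio of 2 (Group 1, n=160): 2 (Group 2, n=160): 1 (Group 3, n=80"), with a more even split in waves of fewer than 40. BIBLIO is Group 3, the smallest planned arm.

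**The concern.** A flat Bonferroni level treats the three nulls as unrelated. If the three contrasts refer to the same three means, they are linked: if SMALL differs from BIBLIO, LOSS cannot equal both of them. After one correct rejection, at most one true null is left, and it can be tested at the full .05.

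The flat rule leaves that allowance unused. When exactly one pairwise null is true, which is the sponsor's own hypothesis (both arms work, and equally well), its family-wise error is only .017. The loss falls mainly on the second BIBLIO comparison. That matters because the SAP expects both active arms to beat BIBLIO, and both comparisons lean on the 80-person arm.

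**Working it through.** **The plan's own figure.** .05/3 = .01667, which is .017 at three decimals. The simple Bonferroni sum is 3 × .017 = .051, but the three contrasts are correlated, so the actual family-wise error is lower (below).

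**Inputs from the documents.** Three contrasts and .017 (SAP); 160/160/80 (Protocol).

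**Assumed, because the documents do not give them.** Two-sided tests; benefit over BIBLIO of 1.5 to 3.0 kg; SD 4 to 8 kg; independent observations; no loss to follow-up unless stated.

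**Direct check of the flat rule** (2.5 kg, SD 6):
- SE of a BIBLIO contrast = 6 × √(1/160 + 1/80) = 0.822 kg
- Expected z = 2.5/0.822 = 3.04
- Two-sided critical value at .017 = 2.387
- Power = Φ(3.043 − 2.387) = Φ(0.656) = 74%

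**Rules compared**, by simulating three independent normal arm means with known SD, 2,000,000 runs per scenario:
- Flat: reject each p < .017.
- Shaffer: if the smallest p ≤ .05/3, reject it and any other p ≤ .05.
- Ordinary Holm: ordered p-values against .05/3, .025, .05.
- Gated Holm: Holm at .05 on the two BIBLIO contrasts; SMALL-LOSS at .05 only if both are rejected.

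**Family-wise error.** All three arms equal: flat .044, Shaffer .043. Exactly one pairwise null true: flat .017, Shaffer at most about .050.

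**Both arms 2.5 kg, SD 6, 160/160/80:**

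| Rule | Each BIBLIO contrast | Both | At least one | False SMALL-LOSS |
|---|---|---|---|---|
| Flat .017 | 74% | 64% | 85% | .017 |
| Ordinary Holm | 77% | 69% | 85% | .037 |
| Shaffer | 81% | 76% | 85% | .048 |
| Gated Holm | 83% | 78% | 88% | .028 |

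**Sensitivity, power per BIBLIO contrast, flat vs Shaffer, equal benefit in both arms:**
- 2.5 kg: SD 4, 98.5% vs 99.3%; SD 5, 90% vs 93%; SD 7, 59% vs 66%; SD 8, 46% vs 53%.
- 2.0 kg, SD 6: 52% vs 59%.
- 2.5 kg, SD 6, 20% loss (128/128/64): 63% vs 70%.
- 2.5 kg, SD 6, near-even arms (133/133/134, the extreme of the small-wave rule): 85% vs 90%.
- If group delivery adds a common design effect, (7/6)² = 1.36 at SD 6 gives the SD 7 figures and (8/6)² = 1.78 the SD 8 figures.

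**Unequal effects, SD 6:**
- 3.0 and 1.5 kg: stronger arm 90% vs 91%, weaker arm 29% vs 44%.
- Only one arm works (2.5 kg): its power against BIBLIO is 74% flat, 84% Shaffer, 79% gated Holm. Power for the true SMALL-LOSS difference is 94% with Shaffer and about 3% with gated Holm.

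**Why one model is needed.** The link between the nulls holds only if all three contrasts are differences among the same three adjusted means. If they came from separately adjusted models, two nulls could both be true after one correct rejection, each tested at .05, and the bound would be 2 × .05 = .10.

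**The case against.** The strongest reply is that nothing is broken. The rule is prespecified, standard and valid, needs no link between the nulls, and gives simple matching simultaneous intervals. All of that stands, and it is why this is an optional improvement.

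A reader might infer from 3 × .017 = .051 that the plan overspends its error. It does not: the simulated rate is .044. A reader might also infer that Shaffer needs only valid pairwise p-values. It does not follow: the SAP's reference to two separate models, with covariates chosen as needed, does not guarantee one common set of means. The flat rule is indifferent to this.

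Shaffer is also not the best rule for every aim. When both arms work equally, gated Holm beats it on every BIBLIO measure and has fewer false SMALL-LOSS findings. When only one arm works, it is worse. That disputes which stepwise rule to choose; it does not favour the flat .017 on power.

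Finally, the SAP hypothesizes no SMALL-LOSS difference, and Shaffer raises the false rejection rate for exactly that contrast. This is a real trade, within the .05 limit.

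**Conclusion.** The flat .017 is valid and conservative. With one three-arm model, a Shaffer step-down keeps family-wise error at or below .05. At 2.5 kg in both arms and SD 6 it gains about 6 points per BIBLIO contrast and about 13 points for winning both. It gives no gain in the chance of at least one BIBLIO win when the arms work equally.

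The error-rate results do not depend on the assumed effect size, except where a particular alternative is named. The power gains do: across the equal-benefit scenarios at 160/160/80 they run from under 1 point (SD 4) to about 7 points per contrast. Two-sided testing is assumed because the SAP does not state sidedness.

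The documents do not support reading this as an invalid analysis or as evidence that the trial is underpowered; they state no power target, effect size or SD. Nor would a non-significant SMALL-LOSS result show equivalence under any of these rules.

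**What to change.** If arm-level outcomes have not been seen, amend the SAP to state:

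1. All three contrasts come from one regression model containing all three arms and one common covariate set, with two-sided tests. This is a precondition for the Shaffer rule.
2. The smallest of the three p-values is tested at .05/3; if it is rejected, the other two are tested at .05 each.
3. Adjusted p-values are reported with 95% confidence intervals.

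If the contrasts stay in separate models, use ordinary Holm (.05/3, .025, .05), which needs no link between the nulls and still gains: 74% to 77% per BIBLIO contrast and 64% to 69% for both. Gated Holm is an equally valid choice if the BIBLIO contrasts matter most and little power for SMALL-LOSS is acceptable when only one arm works.

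The change costs SAP wording only: no participants, visits or data. Its downsides under Shaffer:
- The false SMALL-LOSS rate rises from .017 to about .048 when both arms work equally (2.5 kg, SD 6). The .05 cap is unconditional; among trials with at least one BIBLIO win, the rate goes from .019 to .057.
- If only one arm works, false rejection for the other arm against BIBLIO rises from .017 to .050.
- A smallest p between .0167 and .017 is no longer significant (about 0.2% of trials at 2.5 kg, SD 6).
- Simple simultaneous intervals no longer match the decisions.

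The SAP is dated January 2019 and was uploaded in April 2022. The documents do not show whether outcomes were still unseen, so the sponsor must confirm that first. If they have been seen, keep the flat .017.

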- 2) Participants will be encouraged to engage in **daily dietary intake and physical activity self-monitoring** using a website or app, as these electronic tools facilitate self-monitoring (84).
- 3) Like the participants in Group 2, participants will be given a **BodyTrace™ e-scale** at randomization and will be asked to **weigh themselves daily**. Each time a participant weighs, the e-scale will upload the weight automatically to a secure database, so that timely tailored feedback on weighing frequency/progress can be provided by the interventionist each week through email.
- 4) **Lesson materials** for each session will be drawn from the Look AHEAD ILI and will cover core concepts of weight management (e.g., self-monitoring, exercise, portion size estimation, stress management, stimulus control, goal setting, problem solving).
- 5) **Meal replacements** will be provided to participants for 8 weeks as a method to achieve the study's calorie and fat goals and as a strategy to control portions. Participants will be encouraged to replace 2 meals (typically breakfast and lunch) with a meal replacement and will be advised to consume a third meal of conventional foods as well as additional fruits and vegetables until they reach their daily caloric goals.
- 6) Participants will be provided with **graded physical activity goals** to reach the goal of at least 175 minutes of moderate intensity exercise (e.g., brisk walking) per week (83), similar to physical activity goals set in a previous weight management trial with smokers (67), or 10,000 steps per day. Participants will be provided with **Fit Bit activity trackers** to self-monitor their steps, consistent with the Look AHEAD protocol (83)

Bibliotherapy Condition (Group 3). Participants randomized to Group 3 will wait for 8 weeks before initiating the same smoking cessation intervention as the other two conditions, while they review the provided weight management focused book.

Intervention Components:

- 1) At randomization, participants will receive the **EatingWell Diet book**, as a minimal intervention that will provide information regarding weight management.
- 2) Like the participants in the other conditions, participants will be given a **BodyTrace™ e-scale** at randomization and will be asked to weight themselves daily. However, they will not receive interventionist feedback about their weighing frequency or weight trajectory

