Safety Measures: We will assess depressive symptoms using the 20-item **CESD-R scale (75)**, which is a validated and frequently used self-report measure of depressive symptoms. Scores ≥ 16 are considered to be suggestive of clinically significant depression. In the event that someone reports worsening depression, suicidal ideation, or an adverse event, we will involve the study physician, [name]. At measurement visits and monthly medication calls, we will assess adverse events and suicidality using the **C-SSRS (76)**. We have a safety plan for management of depression and suicidal ideation, including follow-up to ensure that care has been obtained.

Intervention & Varenicline Adherence: Process variables will be a critical element of the data collected, both to assure treatment fidelity and to inform potential dissemination of the intervention.

Interventionists will carefully monitor session attendance, dietary/physical activity/weight self-monitoring (if in Groups 1 or 2), meal replacement utilization (if in Group 2), and varenicline utilization to monitor implementation and to capture intervention exposure. Treatment engagement is a

consistent predictor of weight management success in our work and others (38, 97, 98); thus, we expect that treatment engagement will also be important in the management of postcessation weight gain.

Program Satisfaction: Program satisfaction will be assessed to offer insight into program acceptability for each of the conditions and get feedback on specific intervention components. We propose to adapt the treatment satisfaction measure we are currently using in the Fit Blue study (39), which will inform program refinement and future implementation.

References

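### The adjusted abstinence odds ratios condition on process measures that appear to be post-randomisation adherence, so they need not estimate the intention-to-treat effect

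*SAP*

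**What the plan says.** The last paragraph of the SAP's Statistical Analysis section covers smoking cessation. It hypothesises that the three arms will quit at similar rates at 12 months and gives no margin. Prolonged abstinence is tested first by chi-square, then by logistic regression with BIBLIO as reference. On the purpose of that model the SAP says: "We will estimate the relative odds of a treatment effect on prolonged abstinence". The adjustment list starts with baseline demographics and smoking history and ends "use of tobacco products), process measures and other potential confounders". The same model has a second use: "we can test the associations and estimate effects of additional variables, besides treatment effect". The SAP does not say what the process measures are.

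The opening of the same section puts all outcomes on an intention-to-treat basis, "including available data from all randomized cases, regardless of treatment adherence and smoking status".

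The protocol uses a similar term under Study Measures, in the paragraph headed Intervention & Varenicline Adherence: "Process variables will be a critical element of the data collected". It lists attendance at sessions; diet, activity and weight "self-monitoring (if in Groups 1 or 2), meal replacement utilization (if in Group 2"); and "varenicline utilization to monitor implementation and to capture intervention exposure". Table 1 of the protocol marks intervention adherence for Groups 1 and 2 only during the weight-management and booster phases, and for everyone during the cessation phase. The Bibliotherapy Condition paragraph adds that Group 3 also receives the e-scale "at randomization and will be asked to weight themselves daily". SMALL, LOSS and BIBLIO in the SAP are the protocol's Groups 1, 2 and 3.

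**The concern.** A variable that arises after randomisation cannot confound a randomised comparison. It may lie on the path from assignment to quitting, or share causes with quitting such as motivation. Conditioning on it changes the question from the effect of being assigned to a programme to a contrast at equal adherence, and that contrast is no longer protected by randomisation. The SAP nevertheless calls the result a treatment effect and groups process measures with confounders.

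The direction matters because the hypothesis is similarity. Suppose a weight programme lowered quitting by reducing attendance at cessation sessions or use of varenicline. Adjustment would remove that harm and make the arms look alike. Conversely, if adherence and quitting share a cause and assignment shifts adherence, a difference can appear where there is none. The plan does not say how to read the odds ratios if they disagree with the chi-square test.

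There is also a structural problem. Diet and activity self-monitoring and meal replacement use have no counterpart in BIBLIO, the reference arm.

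**Working it through.** The plan states no abstinence rate, odds ratio or power for this analysis, so there is no figure to reproduce. The only inputs taken from the documents are the 160/160/80 allocation (protocol, Study Project Procedures) and a 5% level, reading abstinence as one of the SAP's other associations. All effect sizes below are assumptions.

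**1. When the two odds ratios differ.** For measures shared by all arms (cessation-session attendance, varenicline use), the adjusted odds ratio departs from the intention-to-treat one, beyond ordinary non-collapsibility, when two things both hold: assignment changes the measure, and the measure is associated with abstinence given arm.

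**2. Harm acting wholly through adherence.** Let A = shift × active + N(0,1) and logit P(abstinent) = −0.9 + k·A. The effect through adherence is about exp(shift × k); the marginal odds ratio is slightly nearer 1. Odds ratios are from 4,000,000 simulated participants. Rejection rates are from 4,000 trials of 160/160/80.

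| shift (SD), k | exp(shift × k) | total OR | adjusted OR | chi-square rejects | adjusted 2-df test rejects | tests disagree |
|---|---|---|---|---|---|---|
| −0.2, 0.4 | 0.92 | 0.93 | 1.00 | 6.4% | 5.4% | 2.9% |
| −0.2, 0.8 | 0.85 | 0.87 | 1.00 | 7.4% | 5.0% | 5.5% |
| −0.45, 0.4 | 0.84 | 0.84 | 1.00 | 9.3% | 5.0% | 7.4% |
| −0.45, 0.8 | 0.70 | 0.72 | 1.00 | 18.0% | 4.9% | 16.0% |

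For comparison, adjusting for an equally prognostic measure with no shift between arms already gives disagreement of 1.6% (k = 0.4) and 2.9% (k = 0.8), from 3,000 replicates.

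**3. No true effect, shared cause.** Let logit P(abstinent) = −0.9 + m·U (about 30% abstinent) and A = shift × √(m²+1) × active + m·U + N(0,1). Replacing U by its expectation given A and arm gives an adjusted log odds ratio of about −m² × shift/√(m²+1). For m = 0.8 and shift +0.45 this is −0.64 × 0.45/1.281 = −0.225, an odds ratio of 0.80; the simulation gives 0.81.

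| m | shift +0.45 | +0.2 | 0 | −0.2 | −0.45 |
|---|---|---|---|---|---|
| 0.4 | 0.94 | 0.97 | 1.00 | 1.03 | 1.07 |
| 0.6 | 0.88 | 0.94 | 1.00 | 1.06 | 1.14 |
| 0.8 | 0.81 | 0.91 | 1.00 | 1.10 | 1.23 |

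At trial size, false rejection for SMALL against BIBLIO is 5.0% to 5.6% at m = 0.4 with a shift. At m = 0.8 it is 5.8% to 6.3% for shifts of ±0.2 and 10.3% to 10.5% for ±0.45. Unadjusted, it is 4.4% to 6.0%. If adherence shifts but is unrelated to quitting, the adjusted ratio stays at 1.00.

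**4. Separate check with binary adherence.** Take abstinence of 23.15% without adherence and 47.47% with it (odds ratio 3), and adherence of 50% in BIBLIO and 70% in the active arm.
- BIBLIO: 0.5 × 0.2315 + 0.5 × 0.4747 = 0.353.
- Active: 0.3 × 0.2315 + 0.7 × 0.4747 = 0.402.
- Total odds ratio: (0.402/0.598)/(0.353/0.647) = 1.23. Given adherence it is 1.00 by construction.
- At 160 v 80, rejection falls from 11.9% to 4.9% with adjustment.
- With no effect and a shared cause, the adjusted ratio is 0.97 to 0.89.
- With no effect and no shift in adherence, both ratios are 1.00.

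**5. Measures with no BIBLIO counterpart.** The SAP's imputation rule concerns outcome data. If diet or activity self-monitoring is left missing in BIBLIO, a complete-case fit loses all 80 planned BIBLIO participants. With meal replacement use it loses 160 + 80 = 240 of 400. In either case no odds ratio against BIBLIO can be estimated. Coding these items as zero in BIBLIO, which the documents do not propose, gives adjusted ratios of 0.72 to 0.25 under no effect in the cases tried. That is a conditional worst case. Weighing frequency is different, because BIBLIO also has the scale.

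**The case against.** - **The premise is an inference.** The SAP says process measures, the protocol says process variables, and neither document refers to the other. This stands. But the protocol paragraph is the only account of such variables in either document, and no baseline measure carries that name. If something else was meant, the covariates still need to be listed.
- **The intention-to-treat clause says who is analysed, not which covariates may enter a model.** Read literally, that is mostly right: a model containing adherence can include every randomised participant. The tension is with the aim of that clause, since an odds ratio at equal adherence is not an effect regardless of adherence.
- **An unadjusted comparison is already planned, and the model has a second, legitimate purpose.** Both are true. The chi-square test is untouched, and studying other predictors is reasonable. But the chi-square test gives no odds ratio, and the SAP presents this model's odds ratio as the treatment effect.
- **The larger figures come from corner cases.** This is fair. The adjusted 1.00 under full mediation follows by construction. Part of the disagreement at a 0.2 SD shift is ordinary adjustment. False rejection near 11% needs both the largest shift and the strongest shared cause. All arms get the same cessation programme and drug, and nothing in the documents shows that adherence will differ.
- **Some movement of an odds ratio is non-collapsibility, not bias.** True: with adherence unaffected by arm, a marginal 1.64 becomes 1.73. This cannot explain a true 1.00 becoming 0.81 or 1.23.
- **An analyst would notice if BIBLIO dropped out of the model.** Probably, but the coding rule would then be chosen after the data were in hand.

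**Conclusion.** The concern holds. As written, the model that yields the SMALL and LOSS odds ratios adjusts for variables that, on the most natural reading, are post-randomisation adherence, so its output need not match the intention-to-treat effect. Under the assumed inputs, real harm with a total odds ratio of 0.93 to 0.72 can be adjusted to 1.00, in the direction of the hypothesis. A true 1.00 can move to between 0.94 and 1.07 with a weak shared cause, or between 0.81 and 1.23 with a strong one. Effects on test error are small except at the extremes.

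The size depends on assignment changing adherence, which the documents neither show nor exclude. The problem is confined to the adjusted abstinence odds ratios and how they are read against the chi-square test; it does not touch that test or the weight contrasts at 0.017. It should be corrected, with medium confidence because the meaning of process measures is inferred.

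**What to change.** In the SAP's abstinence paragraph:

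1. Remove process measures from the model that estimates the treatment effect, and limit the other potential confounders to variables measured before randomisation.
2. Estimate the SMALL and LOSS odds ratios against BIBLIO with arm, baseline demographics and smoking history, and report them beside the chi-square test.
3. List the process measures by name.
4. Keep the second aim by analysing process measures in separate models labelled exploratory, each within the arms where the measure is collected, and do not present those results as treatment effects.

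The cost is a change of SAP wording and a little more analysis. No new data are needed, and the process analyses are kept.
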